## 4.6 Efficacy endpoints

For further details on efficacy endpoints, see Section 14 (Appendix II) of the protocol. For the evaluation of tumor-response related endpoints, response is assessed by investigator and BIRC according to RECIST 1.1.

Response and progression evaluation will be performed according to the Novartis RECIST 1.1 guidelines, included in Section 14 (Appendix II) of the LDK378A2203 protocol.

The text below gives more detailed instructions and notes needed for programming of the analyses described in [Sections 2.7](#) and [2.8.1](#).

### 4.6.1 Implementation of RECIST Guidelines

#### Disease progression

PD should only be assigned if it is confirmed by an objective assessment method as per RECIST 1.1 (e.g. radiologic scan, histology for bronchoscopy, photos for skin lesions) If a new lesion is detected using an objective assessment method other than radiologic scan, it should be entered on the 'New lesion' RECIST eCRF with appropriate method (or method='Other').

In particular, discontinuation due to disease progression or death due to progressive disease, without supporting objective evidence (as defined above), will not be considered as PD in the determination of BOR, the derivation of any efficacy endpoint or efficacy analysis.

### **Change in imaging modality**

Per RECIST 1.1, a change in methodology can be defined as either a change in contrast use (e.g. keeping the same technique, like CT, but switching from with to without contrast use or vice-versa, regardless of the justification for the change) or a change in technique (e.g. from CT to MRI, or vice-versa), or a change in any other imaging modality. A change in methodology will result by default in a UNK (unknown) overall lesion response assessment. However, a response assessment other than the Novartis calculated UNK response may be accepted from the investigator or BIRC if a definitive response assessment can be justified based on the available information. Potential discrepancies between the modality used and overall lesion response reported by the investigator (e.g. change in modality but investigator assessment of response is different from UNK) will be queried during the data validation process.

### **Determination of missing adequate tumor assessments**

For the computation of ORR, patients without any radiological assessment after the start date of study drug will be counted as failure.

Partial or complete responses reported prior to any additional anticancer therapy will be considered for ORR computation in respect of the number of missed assessments before response. In this section, the 'missing adequate assessment' is defined as assessment not done or assessment with overall lesion response equal to UNK. For the sake of simplicity, the 'missing adequate assessment' will also be referred as 'missing assessment'.

As detailed in Section 14 (Appendix II) of the LDK378A2203 protocol, the PFS censoring and event date options depend on the presence and the number of missing tumor assessments. *For example, an event occurring after two or more missing assessments is censored at the analysis of PFS at the last adequate tumor assessment before the event date.*

An exact rule to determine whether there is none, one or two missing assessments is therefore needed. This rule will be based on the distance between the last adequate tumor assessment date and the event date.

If the distance is larger than threshold D1 or D2 then the analysis will assume one or two missing assessments, respectively. The threshold D1 will be defined as the protocol specified interval between the tumor assessments plus the protocol allowed window around the assessments. Similarly, the threshold D2 is defined as two times the protocol specified interval between the tumor assessments plus the protocol allowed window around the assessments. In this study, the protocol defined schedule of tumor assessment is every 8 weeks and each assessment is expected to be performed at the scheduled time point plus or minus 1 week, i.e. the window is 2 weeks, then any distance larger than  $D1 = 8 + 2 = 10$  weeks means one missing assessment and any distance larger than  $D2 = (2 * 8) + 2 = 18$  weeks means two missing assessments.

The same definition of D2 will be used to determine the PFS censoring reason. If the distance between the last adequate tumor assessment date and one of the following dates is  $\leq$  D2:

1. Analysis cut-off date
2. Start date of farther anti-neoplastic therapy
3. Visit date of study treatment discontinuation due to consent withdrawal
4. Visit date of study treatment discontinuation due to loss to follow-up

then the associated censoring reason will be

1. Ongoing
2. New cancer therapy
3. Withdrew consent
4. Loss to follow-up

However, if this distance is larger than D2, then the censoring reason will be 'Adequate assessment no longer available'.

### **Non-measurable disease at baseline**

As specified in Section 14 (Appendix II) of the LDK378A2203 protocol, the RECIST 1.1 criteria imply that only patients with measurable disease at baseline should be included in the study. If a patient without measurable disease is enrolled, the intent-to-treat (ITT) principle requires including these patients in the analyses. Hence, analyses will be based on FAS including patients with either measurable or non-measurable disease. Therefore, a rule needs to be specified on how to handle these cases.

As specified in Table 3-1 of Section 14 (Appendix II) of the LDK378A2203 protocol, overall lesion response can be derived for patients without measurable disease at baseline.

Target lesion response will always be UNK due to missing baseline measurements. Therefore, a CR, PR or SD can never be assigned as an overall lesion response. However, a PD can still be determined from non-target lesions or from new lesions.

As a result, the overall lesion responses will always be UNK until PD occurs. The BOR will either be UNK or PD depending on the timing of PD (if PD is observed  $>$  17 weeks, it will be considered as UNK). The PFS censoring and event date options will depend on how many UNKs precede the PD.

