## Duration of response

Among patients with a confirmed response (PR or CR), DOR is defined as the time from first documented response (PR or CR) to the date of first documented PD or death due to underlying cancer. If a patient has not had an event, DOR is censored at the date of last adequate tumor assessment.

The censoring and event date options to be considered for the main analysis are presented in [Table 2-1](#).

Table 2-1 Outcome and event dates for DOR and PFS analyses

	Situation	Date	Outcome
A	No baseline assessment	Date of first dose of study drug*	Censored
B	Progression at or before next scheduled Assessment	Date of progression	Progressed
C1	Progression or death after exactly one missing assessment	Date of progression (or death)	Progressed
C2	Progression or death after two or more missing assessments	Date of last adequate assessment†	Censored
D	No progression	Date of last adequate assessment •	Censored
E	Treatment discontinuation due to 'Disease progression' without documented progression, i.e. clinical progression based on investigator claim	N/A	Information ignored. Outcome derived based on radiology data only.
F	New anticancer therapy given	Date of last adequate assessment •	Censored
G	Deaths due to reason other than deterioration of 'Study indication'	Date of last adequate assessment •	Censored (only applicable to DOR)

• The rare exception to this is if the patient dies no later than the time of the second scheduled assessment as defined in the protocol in which case this is a PFS event at the date of death

• After the last adequate tumor assessment. "Date of next scheduled assessment" is defined in Section 3.2.7 of Section 14 (Appendix II) of the LDK378A2203 protocol

DOR will be described in tabular and graphical format using Kaplan-Meier methods including estimated median (in months) with 95% CI, 25th and 75th percentiles (Brookmeyer and Crowley 1982, Klein and Moeschberger 2005) and Kaplan-Meier estimated probabilities with confidence intervals (Kalbfleisch and Prentice 2002) at several time points (including at least 4, 8, 12, 15, 18 months).

These analyses will be performed separately based on investigator assessment and based on BIRC assessment.

Refer to Section 4.6.3 for further details regarding derivation of Kaplan - Meier estimates.

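### PFS rule for patients without measurable disease at baseline: performed, progression-free scans coded UNK count as missed, so later progressions are censored with essentially no follow-up

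*SAP*

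**What the plan says.** Four places in the SAP combine.

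- **SAP 4.6.1, Non-measurable disease at baseline.** If such a patient is enrolled, the full analysis set keeps the patient on intent-to-treat grounds. Target response is UNK because there is no baseline measurement. Then: "As a result, the overall lesion responses will always be UNK until PD occurs". On PFS: "The PFS censoring and event date options will depend on how many UNKs precede the PD".
- **SAP 4.6.1, Determination of missing adequate tumor assessments.** Here "the 'missing adequate assessment' is defined as assessment not done or assessment with overall lesion response equal to UNK". On counting: "This rule will be based on the distance between the last adequate tumor assessment date and the event date".
- **SAP Table 2-1, row C2.** "Progression or death after two or more missing assessments" is censored at the last adequate assessment. Protocol 10.5.2 has the same rule. Row D censors a patient without progression at the last adequate assessment too.
- **SAP 2.8.1, Disease control rate.** Non-CR/Non-PD is an allowed best overall response, by investigator and by the blinded independent review committee (BIRC).

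SAP 4.6.2 derives PFS from the overall response that the reader reports (Source 1 investigator, Source 3 BIRC), not from the calculated response (Source 2).

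**The concern.** The missing-assessment rule exists because a PD found after a long unobserved gap cannot be dated well. A scan that was done on time, read, and showed stable non-target disease leaves no such gap. Coding it UNK and then treating UNK as not done makes an observed interval look unobserved.

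Whether the event counts then depends on how long the patient stayed progression-free: early PDs remain events and later ones are removed. That is outcome-dependent censoring. It also works against the reason the SAP gives for keeping these patients, because most of their follow-up is discarded. A patient scanned for years without PD contributes nothing either.

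The SAP is also inconsistent. A best response of Non-CR/Non-PD cannot arise if every response is UNK until PD. A programmer cannot tell whether a reported Non-CR/Non-PD stands or is overwritten.

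**Working it through.** **1. The plan's thresholds.** Inputs from SAP 4.6.1: "the protocol defined schedule of tumor assessment is every 8 weeks", with scans allowed "plus or minus 1 week, i.e. the window is 2 weeks".

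- D1 = 8 + 2 = 10 weeks (beyond this, one missing assessment).
- D2 = 2 × 8 + 2 = 18 weeks (beyond this, two missing assessments).

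Both match the SAP.

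**2. Applying the rule.** No scan before PD can be adequate, so the last adequate assessment is at best the baseline scan. The SAP does not say whether distance then runs from first dose or from that scan. Protocol 7.2.1.1 sets the baseline scan within 28 days before enrollment and accepts routine scans up to 6 weeks before treatment. With ±1 week on each scan:

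| PD found at | UNKs before PD | Distance from first dose (weeks) | From scan 4 weeks pre-dose | From scan 6 weeks pre-dose |
|---|---|---|---|---|
| Scan 1 (weeks 7-9) | 0 | 7-9: event | 11-13: event | 13-15: event |
| Scan 2 (weeks 15-17) | 1 | 15-17: event | 19-21: censored | 21-23: censored |
| Scan 3 (weeks 23-25) | 2 | 23-25: censored | 27-29: censored | 29-31: censored |
| Scan 4 (weeks 31-33) | 3 | 31-33: censored | 35-37: censored | 37-39: censored |

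Scan 1 always counts (beyond D1 it falls under row C1, still an event). From scan 3 on, PD is always censored. Scan 2 depends on the origin; measured from the baseline scan, the distance rule also disagrees with the UNK count. The censoring date is at or before the start of PFS time.

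**3. After the fix.** If the previous progression-free scan is adequate, the distance to PD is 8 weeks on schedule and 6 to 10 with windows. That does not exceed D1, so no assessment is missing and PD counts on its own date.

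**4. Events lost.** Assumptions, none given in the documents: 4 to 12 of the 124 treated patients affected, exponential PFS with median m = 8, 11 or 18 months, 48 months of follow-up, distance from first dose. One month is 30.4375 days (SAP 4.4), or 4.348 weeks.

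Share lost = exp(−ln 2 × 16 / (4.348 m)) − 2^(−48/m)

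| m (months) | Event after week 16 | Event-free at 48 months | Share lost | × 4 patients | × 12 patients |
|---|---|---|---|---|---|
| 8 | 0.727 | 0.016 | 0.711 | 2.8 | 8.5 |
| 11 | 0.793 | 0.049 | 0.744 | 3.0 | 8.9 |
| 18 | 0.868 | 0.157 | 0.711 | 2.8 | 8.5 |

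**5. Effect on the median.** Under these assumptions, with scan dates varying by ±1 week, simulated Kaplan-Meier medians fall on average by about 0.2 to 0.45 month. The typical (median) shift is under 0.1 month, and the estimate rises in roughly 4 to 18% of single trials. With all scans exactly on the 8-week grid and medians of 7, 11 and 16 months, the average fall is 0.0 to 0.1 month if 2% of patients are affected, about 0.3 if 10%, and 0.7 to 0.8 if 20%.

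**The case against.** The best defence is that the rule will seldom operate. Inclusion criterion 10 requires a measurable lesion, and protocol 7.2.1.1 makes patients with only non-measurable lesions ineligible, so investigator cases should be rare. PFS uses the reported response, and a reader who reports Non-CR/Non-PD has not reported UNK, so row C2 need not apply. Appendix II and the imaging charter, which may settle the coding, cannot be seen here. PFS is a descriptive secondary endpoint, the average bias is conservative, and censoring reasons are tabulated. The SAP is dated 12-April-2018, after the 22-Jan-2018 cut-off, so a change could break comparability with the primary report.

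Most of this stands and lowers the severity. It does not remove the fault: the UNK rule and its link to PFS are in the SAP's own text, and the conflict with the disease control definition leaves the coding open.

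A reader might infer more than the text supports:

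- **Censoring at treatment start.** That date is written only for a missing baseline assessment (Table 2-1 row A; SAP 4.6.1, Missing baseline tumor assessment). Here the stated date is the last adequate assessment. The effect is much the same, but the date is inferred.
- **Mainly a BIRC problem.** The BIRC reads independently and might find no target lesion. However, the passage speaks of an enrolled patient without measurable disease and does not mention a central reader who selects none in an eligible patient.
- **Median PFS always falls.** It does on average, not in every trial.

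**Conclusion.** The concern holds as a minor point. As written, PD or death after two or more performed, non-progressing UNK scans is not a PFS event and is censored with essentially no follow-up. PD at the first scan counts; PD at the second depends on an origin that the SAP leaves open. Where a reader reports Non-CR/Non-PD, the rule may not bind.

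The size rests on the assumed 4 to 12 affected patients: about 3 to 9 lost events and an average fall of about 0.2 to 0.45 month, well below the scan interval of 8 / 4.348 = 1.8 months. If no patient is affected, nothing changes. The response rate and the primary decision are untouched. Duration of response is untouched as well, because under 4.6.1 these patients cannot be assigned a response.

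**What to change.** In SAP 4.6.1, reconcile the non-measurable-disease paragraph with the disease control rate definition:

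- For the PFS missing-assessment count, treat a performed, evaluable scan with non-target disease and no progression as adequate (Non-CR/Non-PD).
- Keep UNK for scans not done or not evaluable.
- Apply Table 2-1 rows B, C1 and C2 to that sequence.
- State whether the rule also applies when the BIRC reader finds no target lesion, and from which date distance is measured when no post-baseline scan is adequate.
- Leave the response-rate and duration-of-response rules as they are.
- Check the change against Appendix II, and report PFS under the present UNK-as-missing rule as a sensitivity analysis for comparability with the primary clinical study report.

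The cost is a short text change, a small programming change and one extra PFS table. No new data should be needed if non-target responses are recorded as RECIST 1.1 reading implies. Main PFS may differ slightly from the primary report, and because the change follows the cut-off it should be documented in SAP Section 3.

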### **Missing baseline tumor assessment**

As specified in Section 14 (Appendix II) of the protocol (see Table 4-1), since the timing of PD cannot be determined for patients with missing baseline tumor assessment, these patients are censored in the PFS analysis at the start date of treatment. This rule, however, only applies to the 'PD component' of the PFS or DOR assessment.

Patients without baseline tumor assessment who die within D2 distance from start date of treatment will be counted as having an event in the primary analysis of PFS. All deaths will be counted in the OS analysis regardless of presence or absence of the baseline tumor assessment.

### **Construction of waterfall graphs**

The waterfall graphs will be used to depict the anti-tumor activity. These plots will display the best percentage change from baseline in the sum of the longest diameter of all target lesions for each patient. The proportions of patients with various degrees of tumor shrinkage or growth can then represent a useful efficacy metric.

However, caution needs to be paid to the assessments, where an occurrence of a new lesion or worsening in non-target lesions (resulting in PD as an overall lesion response at given assessment) contradicts the measurements obtained on target lesions. These assessments will not be displayed as bars in the graph. If such a "contradicting" assessment represents the only post-baseline assessment for a patient, then the patient will be represented by a special symbol (e.g. \*) in the waterfall graph.

The assessments with unknown target response and also assessments with unknown overall response will be excluded. Patients without any valid assessments will be completely excluded from the graphs.

The total number of patients displayed in the graph needs to be shown and this number will be used as a denominator when calculating the percentages of patients with tumor shrinkage and tumor growth. Footnote will explain the reason for excluding some patients (due to absence of any valid assessment).

All possible assessment scenarios are described in [Table 4-2](#).

**Table 4-2 Inclusion/exclusion of assessments used in waterfall graph**

Criteria for inclusion/exclusion			Possible source of contradictions	
Target response	Overall lesion response	Include in waterfall	Non-target response	New lesion?
CR/PR/SD	PD	Yes but as* only	PD	any
CR/PR/SD	PD	Yes but as* only	any	Yes
UNK	UNK or PD	No	any	any
CR/PR/SD	UNK	No	UNK	No
CR/PR/SD	CR/PR/SD	Yes as a bar	SD/IR	No
PD	PD	Yes as a bar	any	any

The following algorithm will be used to select the graph:

- I. Select "valid" post-baseline assessments to be included, i.e. for each patient and each assessment repeat the following four steps:
  - 1.1 Check the target lesion response and overall lesion response at each assessment. If at least one of them is UNK then exclude the whole assessment. Otherwise, go to step 1.2.
  - 1.2 Check the overall lesion response. If PD then go to step 1.3. Otherwise, go to step 1.4

1.3 Check target response. If it's PD then go to step 1.4. Otherwise flag the assessment \*

1.4 Calculate the % change from baseline in target lesions.

2. For each patient, go through all valid assessments identified in step 1 and find the assessment with best % change from baseline in target lesions. The "best" means best for the patient, i.e. the largest shrinkage or if a patient only has assessments with tumor growth take the assessment where the growth is minimal. (*Example 1*: Patient 1 has the following % changes from baseline at assessments 1, 2, 3, 4 and 5, respectively: -10%; -25%; -13%; -4% and +6%. His/her best % change is then -25%. *Example 2*: Patient 2 has the following % changes from baseline at assessments 1, 2 and 3, respectively: +5%; +18% and +35%. His/her best % change is then +5%.
3. Construct the waterfall graph displaying the best % change from baseline for each patient. Patients having only \* flagged assessment(s) will be displayed separately.

Both investigator assessment and BIRC will be used in the construction of waterfall plot.

The recommended way of the display from left to right is:

1. Bars under the horizontal axis representing tumor shrinkage
2. Bars above the horizontal axis representing tumor growth
3. "Zero" bars with \* symbol representing patients with contradiction

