Imaging evaluations will be performed at the End of Treatment (EOT) visit. If a patient is known to have PD at a scheduled study visit, EOT imaging evaluations do not need to be repeated for the EOT visit.

Imaging assessment by the BIRC

All radiological assessments will be read locally and should be submitted promptly after acquisition to the imaging CRO designated by Novartis. The process at the imaging CRO will ensure that the BIRC remains blinded to the results of the local assessment (and other unblinding information). The decision regarding patient management will remain with the local investigator.

Rapid image transmission to the BIRC may be accomplished by uploading all digital images acquired by the investigator in a secured website.

The results of the BIRC assessment will not be communicated to sites.

All timepoints will be read on an ongoing basis (rolling reads) as detailed in the imaging charter to be provided by the designated imaging CRO.

Duration of post-baseline tumor assessments

Tumor assessments will continue until one of the following events:

- The patient experiences RECIST-defined PD as determined by the investigator AND treatment with LDK378 ceases. If treatment with LDK378 continues beyond RECIST-defined PD, imaging assessments must continue every 8 weeks until LDK378 treatment ceases
- If a patient discontinues study treatment in the absence of PD, tumor assessments will continue to be performed every 8 weeks until the patient experiences a RECIST-defined PD as determined by the investigator
- Death
- Lost to follow-up, or
- Patient decision involving withdrawal of consent (see [Section 7.1.4.1](#)).

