### 2.7.4 Supportive analyses

Listings of calculated overall lesion response based on raw measurements reported by the investigator (Source 2 in Table 4-3) will be generated. Waterfall plots representing the best percentage change from baseline in the sum of the longest tumor diameters for target lesions will be produced.

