## Best overall response

The BOR will be assessed based on reported lesion responses at different evaluation time points. Both CR and PR require confirmation at least 4 weeks after its initial observation.

Only tumor assessments performed before the start of any further anti-neoplastic therapies (i.e. any additional secondary anti-neoplastic therapy or anti-cancer surgery) will be considered in the assessment of BOR. If a patient receives any further anti-neoplastic therapy while on study, any subsequent assessments will be excluded from the BOR determination. Further anti-neoplastic therapies will be identified via protocol deviations or from the data collected on 'Anti-neoplastic therapies since last date of study drug' as appropriate. Clinical deterioration will not be considered as documented disease progression. Patients with BOR 'unknown' will be summarized by reason for having unknown status. The following reasons will be used:

- No valid post-baseline assessment
- All post-baseline assessments have overall response UNK
- New anti-neoplastic therapy started before first post-baseline assessment
- Stable disease (SD) too early ( $\leq 6$  weeks after start date of study drug)
- PD too late ( $> 12$  weeks after start date of study drug)

Special (and rare) cases where BOR is 'unknown' due to both early SD and late PD will be classified as 'SD too early'.

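### The SAP's waterfall algorithm has no cut at the start of new anticancer therapy, so a bar can show shrinkage under another drug

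*SAP*

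**What the plan says.** SAP 2.7.4 lists the plot among the supportive analyses of the primary variable: "Waterfall plots representing the best percentage change from baseline in the sum of the longest tumor diameters for target lesions will be produced". SAP 4.6.1 (Construction of waterfall graphs) states its purpose: "The waterfall graphs will be used to depict the anti-tumor activity".

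The algorithm under Table 4-2 screens assessments in two ways:

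- Step 1.1 looks at the target and overall lesion responses: "If at least one of them is UNK then exclude the whole assessment".
- Step 1.3 deals with an overall response of PD. If the target response is also PD, the assessment goes forward. "Otherwise flag the assessment" with a star, so that it is not drawn as a bar.

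Step 2 then tells the programmer, for each patient, to "go through all valid assessments identified in step 1 and find the assessment with best % change from baseline in target lesions". The same construction serves the investigator and BIRC plots.

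For BOR, SAP 2.8.1 does have a rule on later treatment: "If a patient receives any further anti-neoplastic therapy while on study, any subsequent assessments will be excluded from the BOR determination".

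On imaging, protocol 7.2.1.2 says that for a patient who stops LDK378 without PD, "tumor assessments will continue to be performed every 8 weeks until the patient experiences a RECIST-defined PD as determined by the investigator". The other events listed there that end imaging are death, loss to follow-up and withdrawal of consent. New anticancer therapy is not among them.

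**The concern.** A waterfall plot in a single-arm trial is read as a picture of what the study drug did to the tumours. If scans made under a later therapy are eligible, a bar can belong to the later drug, and nothing on the plot would tell the reader so.

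The direction is fixed. Step 2 keeps the most favourable value, so adding later scans to a patient who already has a bar cannot make that bar worse.

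At stake are the depth of individual bars and the percentages with shrinkage and growth that the SAP derives from the plot. The plot would also follow a different rule on later therapy from the response rate it is meant to support.

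**Working it through.** **1. Reproduce the SAP's own examples.** Applying steps 1 and 2 as written:

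- Example 1: the changes are -10, -25, -13, -4 and +6%. The minimum is -25%, as the SAP states.
- Example 2: the changes are +5, +18 and +35%. The minimum is +5%, as the SAP states.

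**2. Look for a cut at new therapy, endpoint by endpoint.**

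- ORR (SAP 2.7.3, and 4.6.1 on missing assessments): only responses before additional anticancer therapy count.
- BOR (SAP 2.8.1): assessments after the start of further therapy are excluded.
- DOR and PFS (SAP Table 2-1, row F; PFS text in 2.8.1): censored at the last adequate assessment.
- Waterfall (SAP 2.7.4; 4.6.1 text, Table 4-2 and algorithm): no mention.

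Each cut is worded for its own endpoint. SAP 2.7.3 extends its rule on treatment beyond progression to the other efficacy endpoints, but does not extend its new-therapy rule in that way.

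**3. Check that such scans can exist.** Protocol 4.1, 7.1.5.1 and 7.2.1.2 continue imaging every 8 weeks after LDK378 stops without PD. Protocol 6.1.3 leaves later treatment to the physician. The Amendment 3 summary explains that new therapy was removed as a reason to stop imaging so that a PFS sensitivity analysis could ignore it. The current text agrees with that summary.

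**4. Trace a case through the algorithm (assumed data).** A patient has +5% and +8% on LDK378 with stable disease, stops without PD and starts another drug. The next scans show -40% and -45%, with target and overall response PR.

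- As written: no response is unknown and none is PD, so all four scans are valid. The minimum of (+5, +8, -40, -45) is **-45%**.
- With the BOR cut: the minimum of (+5, +8) is **+5%**.

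A second assumed patient has only one valid scan, -40%, made after new therapy. As written, the bar is -40%. With the cut, the patient has no bar.

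**5. Scale.** The documents do not say how many patients are affected. The protocol reports 124 treated patients, which is the most that could be plotted. If k patients moved from growth to shrinkage, the shrinkage percentage would rise by 100 × k/124:

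- k = 1: 0.8 points
- k = 3: 2.4 points
- k = 6: 4.8 points
- k = 12: 9.7 points

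These values of k are assumptions, not estimates. A bar that only deepens, say from -10% to -50%, changes the picture but not this percentage.

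**The case against.** The best case for the plan is that this is silence, not instruction. The SAP nowhere says that scans under later therapy are to be plotted. It cuts at new therapy for every main response and progression endpoint, and the Amendment 3 summary gives a PFS sensitivity analysis as the reason for continued imaging. Table 4-2 lists combinations of response categories and makes no claim about timing. SAP 4.6 also refers to protocol Appendix II for efficacy details. Most of that appendix is not shown, so a general rule there cannot be ruled out.

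Much of this stands. The omission may be an unrepeated convention, and the unseen appendix limits confidence to moderate. But 4.6.1 is written as a programming algorithm with explicit validity steps, and its waterfall text points to no further filter. A program that follows it would use these scans.

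A reader might also take a bar that disagrees with the same patient's BOR as proof of the problem. It is not. BOR needs confirmation at least 4 weeks later, while the bar uses a single scan, so an unconfirmed shrinkage on LDK378 alone can produce the same mismatch.

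Nor is the choice of denominator a hidden bias. The SAP says of the displayed count that "this number will be used as a denominator when calculating the percentages of patients with tumor shrinkage and tumor growth", requires that count to be shown, and asks for a footnote explaining exclusions. Whether to add a percentage on the full analysis set is a matter of preference.

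**Conclusion.** The point holds, with moderate confidence. As written, the waterfall algorithm can credit LDK378 with shrinkage under a later therapy, and for a patient who already has a bar the effect can only be neutral or favourable.

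The number of patients affected is unknown and probably small. To change an existing bar, a patient must usually stop LDK378 without PD, start another therapy, be scanned again before PD, and then show a better change than any reached on LDK378. The documents give no rate for that sequence, so no count of affected bars can be derived from them.

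A reader might infer that the primary result is contaminated. The documents do not support that: ORR, BOR, DOR and PFS have their own cuts, and no test or stopping rule uses the plot. The effect is confined to this supportive display and its shrinkage and growth percentages.

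The conclusion assumes that the unseen part of Appendix II holds no general rule excluding these assessments.

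**What to change.** Add to step 1 of the algorithm in SAP 4.6.1 that any assessment on or after the start of further anti-neoplastic therapy or anti-cancer surgery is excluded, using the same rule and date as BOR in 2.8.1. Apply it to both the investigator and BIRC plots, and footnote how many patients it affects. If Appendix II already contains such a rule, cite it in the waterfall text.

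The cost is one line of SAP text and one program filter, using therapy data already needed for BOR. The downside is that a few bars may become less favourable, and a patient whose only valid scans follow new therapy would drop out of the plot.
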